5.3 Concurrent Medications and Therapies

5.3.1 Allowable Regimens

Subjects may continue their baseline medication(s). The daily dose of each medication will be maintained throughout the study if possible. If for any reason deemed necessary by the investigator, a subject requires additional medication(s), the medication(s) route of administration and the indication for which it was given must be recorded in the source documents. All concomitant medications will be recorded on the appropriate case report form.

Systemic, inhaled and topical steroids used as part of an antiemetic regimen or maintenance-dose for non-cancerous disease are permitted.

5.3.2 Prohibited Medications

Subjects who require the use of strong CYP3A4 inducers (eg, including but not limited to St. John's Wort, dexamethasone, phenytoin, carbamazepine, rifampin, rifabutin, phenobarbital) are not eligible for this study and use of these agents is prohibited as long as the subject is receiving sorafenib in this study.

Subjects will not receive any investigational or noninvestigational cytotoxic chemotherapy, hormonal therapy, biological therapy (including monoclonal antibodies), immunotherapy or any locoregional therapy (such as embolization, RFA or percutaneous ethanol injection) to treat hepatocellular carcinoma during the treatment period. Alternative anticancer therapies may be administered after radiologic disease progression has been documented, but will be avoided if possible during the 30 day safety follow up period after the last dose of study agent (mapatumumab/placebo and/or sorafenib) whichever is last. These medications are allowed in the long-term follow-up period after the 30 day safety follow-up period and documentation of radiologic disease progression.

AM02
23Feb11

5.3.3 Prohibited Therapies

Subjects will not undergo major or elective surgery during the treatment period of the study; if surgery is required, the subject will be withdrawn from study treatment.

6 Study Procedures

6.1 Screening Procedures

The nature of this study and the potential risks and benefits associated with participation in the study will be explained to all potential study subjects. Written informed consent (including consent for the use and disclosure of research-related health information) must be obtained before any screening procedures are performed that are not considered standard of care.

All of the following assessments must be performed within 28 days prior to enrollment:

- Obtain written informed consent for participation in the study.
- Obtain informed consent for participation in the optional biomarker sub-study.
 - If consented, obtain tissue block/slides or cell pellet from diagnostic histologic/ cytologic sample.
- Record demographics.
- Obtain medical history, to include history of all treatments used to treat the current cancer and all prior cancer treatments.
- Perform baseline complete physical examination including body weight and height.
- Assess vital signs (blood pressure, heart rate, respiratory rate and temperature).
- Evaluate performance status (ECOG scale; see [Appendix 3](#)).

- Draw blood for laboratory tests (see [Appendix 7](#)): complete blood count with differential, chemistry, hepatitis B surface antigen, Hepatitis B virus DNA, hepatitis C antibody and testing for serum pregnancy (all females with an intact uterus [unless amenorrheic for the previous 24 months] regardless of age).
- Obtain radiologic disease and AFP assessments. The method of disease assessment, as per mRECIST for HCC (see [Appendix 5](#)), will be consistent throughout the study.
- Obtain electrocardiogram.
- Record medications used within 28 days before enrollment.
- Confirm that subject meets all inclusion/exclusion criteria.

6.2 Study Enrollment/Randomization Procedures

Subjects that meet the eligibility criteria will be randomly assigned treatment by a central interactive voice response system in a 1:1 ratio to 1 of 2 treatment arms. The randomization will be stratified according to BCLC advanced stage C vs BCLC intermediate stage B and ECOG performance status (0 vs 1, 2). The 1st planned dose of sorafenib and mapatumumab/placebo will be administered no more than 3 days following randomization and not prior to randomization. All study site personnel (with the exception of the unblinded site pharmacist or unblinded designee), the subject, and the Sponsor will remain blinded to the study agent received.

6.3 On-treatment Study Procedures

Table 6-1 Study calendar

Procedure	Footnotes	Screen Phase	Cycle 1					Cycle 2					Additional Cycles ¹³			Extended Access Phase	Safety Follow-up Phase
			Day 1	Day 2	Day 3	Day 8	Day 15	Day 1	Day 3	Day 8	Day 15	Day 1	Day 8	Day 15			
Informed consent		X														X	
Laboratory																	
CBC with differential; Coagulation parameters	1	X	X	X	X	X	X	X	X	X	X	X	X	X	X		
Chemistry	1	X	X	X	X	X	X	X	X	X	X	X	X	X	X		
Pregnancy	2	X	X														
Hepatitis	1	X															
B and T lymphocyte subsets	3		X					X	X			X					
Immunogenicity	4		X					X				X					
Pharmacokinetics	5		X			X		X				X					
Biomarkers	6		X	X	X	X	X	X	X	X	X						
Study Agent Admin																	
Sorafenib	7							Twice daily					X				
Mapatumumab/Placebo	7		X					X				X			X		
Physical/Clinical																	
Med Hx / Phys.Exam	-	X															
Vital signs	8	X	X			X	X	X		X	X	X			X		
Body weight	9	X	X					X				X					
Performance Status	10	X	X					X				X					
Record AEs/	11	X											<-----Throughout the study----->				

Table 6-1 Study calendar

Procedure	Footnotes	Screen Phase	Cycle 1				Cycle 2				Additional Cycles ¹³			Extended Access Phase	Safety Follow-up Phase
			Day 1	Day 2	Day 3	Day 8	Day 15	Day 1	Day 3	Day 8	Day 15	Day 1	Day 8	Day 15	
Conmeds															
Disease Assessments	12	X	Performed at the end of every 2 cycles (ie, Cycles 2, 4, 6) and every 2 cycles thereafter until radiologic PD is documented.										X		
α – Fetoprotein (AFP)	12	X	Performed at the end of every 2 cycles (ie Cycles 2, 4, 6) and every 2 cycles thereafter until radiographic PD is documented.												
ECG	-	X	Repeat as clinically indicated												

AE = adverse event; CBC = complete blood count; CT = computerized tomography; ECG = electrocardiogram; PD = progressive disease.

- ¹ Safety Labs: Day 1 (complete blood count with differential, coagulation parameters [INR, PT, PTT] and chemistry) must be performed within 3 days prior to dosing on Day 1 of each cycle. See [Appendix 7](#) for a detailed list of required laboratory assessments.
- ² Pregnancy: Serum test at screening, urine test pre-dose Cycle 1 Day 1; must be negative to receive treatment.
- ³ B and T lymphocyte subsets: Blood samples for quantification of B and T lymphocytes will be obtained in Cycles 1 and 2 only. Samples will be obtained on Day 1 (prior to dosing) and Day 15 of Cycles 1 and 2.
- ⁴ Immunogenicity: Obtain prior to dosing on Day 1 of Cycles 1, 2, 4, 6, every 2 cycles thereafter and at the end of treatment visit (at least 30 days after the last dose). On days when immunogenicity and pharmacokinetic samples are collected they will be collected together.
- ⁵ Pharmacokinetics: Blood specimens will be collected for determination of serum mapatumumab concentrations from subjects as follows: Cycle 1 (on Day 1 prior to the administration mapatumumab/placebo and at the completion of the mapatumumab/placebo infusion, and on Day 8), Cycles 2, 4 and 6 and thereafter on each even cycle (prior to dosing on Day 1, on the day of each disease assessment, and at the end of treatment visit (at least 30 days after the last dose). On days when immunogenicity and pharmacokinetic samples are collected they will be collected together.
- ⁶ Biomarkers: For subjects participating in the optional biomarker sub-study, historical biopsy samples will be collected, if available, and samples will be collected if obtained during the treatment period in Cycle 1 Days 1 (pre-dose mapatumumab), 2, 3, 8 and 15 and Cycle 2 Days 1 (pre-dose mapatumumab), 3, 8 and 15. In addition, blood samples will be obtained as follows: blood for isolation of DNA will be collected once, preferably in Cycle 1. Blood for isolation of serum will be collected in Cycles 1 and 2 (pre-dose on the day of mapatumumab/placebo dosing). Further details on the biomarker sub-study are outlined in [Appendix 6](#).
- ⁷ Study Agent Administration: Sorafenib will be administered at a dose of 400 mg twice daily without food (at least 1 hour before or 2 hours after a meal). On days when both sorafenib and mapatumumab/placebo are administered together, sorafenib should be taken at the same time as any other calendar day.
- ⁸ Vital Signs: Blood pressure will be monitored weekly for the first 6 weeks. Vital signs will be obtained within 30 minutes prior to administration of mapatumumab/placebo and at the end of infusion on Day 1 of each cycle. For subjects in the Extended Access Phase, only BP is required to be monitored and this should be performed every 6 weeks (\pm 3 days).
- ⁹ Body Weight: To be obtained on the day of or within 3 days before dosing on Day 1 of each cycle.
- ¹⁰ Performance Status: Obtained prior to dosing on Day 1 of each cycle.

- ¹¹ Adverse Events: (S)AE collection begins with the start of 1st study agent administration. Concurrent medications will be recorded within 28 days prior to Cycle 1 Day 1. For subjects in the Extended Access Phase, only SAEs will be recorded.
- ¹² Disease and α – Fetoprotein (AFP) Assessments: Radiologic and AFP assessments will be performed at the end of every 2 cycles (ie, Cycles 2, 4, 6, etc). For subjects discontinuing treatment prior to documentation of radiologic disease progression, disease assessments will be performed every 6 weeks (\pm 3 days), starting 6 weeks after the previous disease assessment while on study, until radiologic disease progression is documented. If disease progression is based only on new lesions or is equivocal, images will be provided to the blinded, independent reader for confirmation of disease progression. All imaging scans used for disease assessments will be made available for independent radiology review by the Sponsor or designee. For subjects in the Extended Access Phase, disease assessments will be performed as at least every 3 months or as per standard of care, whichever is sooner, until disease progression is documented. Independent radiological review of response or for confirmation of disease progression is not required.
- ¹³ Subjects who discontinue mapatumumab/placebo will complete the current cycle assessments per the study calendar. Subsequently, for subjects in the Extended Access Phase, subjects receiving sorafenib alone will be assessed as per local standard of care and will return at least every 6 weeks for BP monitoring. Serious adverse events will be recorded throughout the study

(concluded)

6.4 Extended Access to Study Drug

Subjects who completed more than 24 months of study treatment sorafenib with or without mapatumumab and who in the opinion of the investigator obtain clinical benefit from treatment, will be allowed to continue treatment with sorafenib with or without unblinded mapatumumab in the clinical trial. Prior to continuing into the Extended Access phase, subjects will be re-consented to agree to the study assessments and a local re-review of their pathology/cytology. This extension of treatment will continue until the subject's disease progresses (Section 6.8) or they withdraw from study (Section 6.7). In addition extension of treatment with mapatumumab will not extend beyond the expiry date of the drug batch (March 2016).

During the Extended Access phase, subjects will have regular visits for disease assessments at least every 3 months or as per standard of care, whichever is sooner, until disease progression is documented. In addition BP will be monitored every 6 weeks and recorded in the eCRF. Serious AEs will continue to be collected during this Extended Access phase according to Section 8. Study drug administration and inventory/accountability will continue to be recorded during this period according to Section 5. Laboratory assessments will be performed as per the standard of care.

6.5 Safety Follow-up

After discontinuation of study treatment, all subjects will return at least 30 days after the last dose of sorafenib and/or mapatumumab/placebo, for scheduled safety follow-up assessments as outlined in [Table 6-1](#).

AM03
15Jul15

6.6 Withdrawal of Subjects from Treatment

Subjects will be free to withdraw from treatment at any time, for any reason, or they may be withdrawn/removed, if necessary, to protect their health (see reasons for withdrawal below). It is understood by all concerned that an excessive rate of withdrawals can render the study uninterpretable; therefore, unnecessary withdrawal of subjects will be avoided.

Subjects may be withdrawn from treatment for any of the following reasons:

- Radiologic disease progression.
- Continued unacceptable toxicities despite optimal treatment or dose reduction.
- Intercurrent illness, at the investigator's discretion.
- Withdrawal of consent.
- Non-compliance/Lost to follow-up.
- Pregnancy.
- Termination of the study by the sponsor.

Following subject withdrawal, every effort will be made to collect safety information on each subject through 30 days following the last dose of study treatment, unless the subject

AM03
15Jul15

withdraws consent and refuses to comply with the protocol stipulated safety follow-up or share information obtained after the date of withdrawal of consent.

6.7 Withdrawal of Subjects from Study

Subjects may be withdrawn from the study for any of the following reasons:

AM03
15Jul15

- Withdrawal of consent.
- Non-compliance/Lost to follow-up.
- Termination of the study by the sponsor.

6.8 Disease Response Assessments

Imaging endpoints will be determined using the modified RECIST criteria for HCC proposed by [Lencioni](#) 2010 mRECIST for HCC is a joint guideline of the American Association for the Study of Liver Diseases and the Journal of the National Cancer Institute.

Lesions which manifest typical imaging characteristics for HCC demonstrate intratumoral arterial contrast on CT and MRI images. mRECIST accounts for newer therapies which may impact tumor vascularity and may not yield a typical cytotoxic decrease in tumor size by incorporating changes in vascularity into the criteria for target lesion response. Diligence in obtaining images during the hepatic arterial contrast enhancement phase is a requirement at baseline and all subsequent scans. The same imaging method must be used at baseline and during follow up.

As in conventional RECIST, overall response is the result of the combined assessment of target, nontarget, and new lesions. There are also specifications for incorporating portal vein thrombosis, portal hepatic lymph nodes, and pleural effusions/ascites into the response assessment. As with conventional RECIST, the appearance of any new lesion overrides any existing lesion response, resulting in classification as progressive disease (PD). Key aspects of mRECIST as adapted for this study are summarized in [Appendix 4](#).

Baseline images will be provided to the BICR for confirmation of radiologic eligibility (measurable disease). Confirmation of radiologic eligibility for the study will be provided to the site by the BICR within 72 hours of receipt of images and will be required for randomization.

Disease assessments and an assessment of α -fetoprotein will be performed at the end of every 2 cycles (ie, Cycles 2, 4, 6 and every 2 cycles thereafter). The response assessment will be performed and documented no more than 5 days before the start of the next cycle. All images will be provided to the BICR following each disease assessment.

If disease progression is based only on new lesions or is equivocal, images will be provided to the BICR for confirmation of radiologic disease progression prior to discontinuing study treatment. PR and CR will be confirmed at the next scheduled disease assessment (no fewer than 4 weeks after the initial documentation of PR or CR).

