5.1.4 Mapatumumab/Placebo Dose Toxicity/Delay

Mapatumumab/placebo will be discontinued for Grade 4 transaminase elevations of any duration if they are considered related to mapatumumab.

AM01
21Dec10

Mapatumumab/placebo may be delayed up to 2 weeks for toxicities considered related to mapatumumab as described below or if the investigator believes that a delay in dosing is warranted in the interest of subject safety.

The National Cancer Institute Common Terminology Criteria for Adverse Events (NCI-CTCAE, Version 4.0) will be used to grade AEs.

- Grade 4 neutropenia for > 7 consecutive days or febrile neutropenia.
- Grade 4 thrombocytopenia.
- Grade 3 or greater non-hematologic AEs except transient transaminase, amylase and lipase abnormalities for which the following criteria will apply:
 - Grade 3 or Grade 4 elevations in transaminases that do not resolve to baseline or Grade 1 before the next cycle.
 - Grade 3 elevations in lipase or amylase associated with clinical/imaging findings of pancreatitis, or resulting in chronic damage to the pancreas.
 - Any Grade 4 elevations in lipase or amylase for > 4 consecutive days.

If mapatumumab/placebo is delayed for toxicity and the toxicity does not resolve (\leq Grade 1) or return to baseline within 2 weeks after the delayed dose was originally scheduled (based on a 21-day treatment cycle), the subject will be withdrawn from further treatment with mapatumumab/placebo. If mapatumumab/placebo is delayed because the investigator believes a delay is warranted in the interest of subject safety and dosing of mapatumumab/placebo is not resumed within 2 weeks after the delayed dose was originally scheduled (based on a 21-day treatment cycle), the subject will be withdrawn from future treatment with mapatumumab/placebo. Sorafenib dosing will continue while mapatumumab/placebo dosing is held. The subject will continue receiving sorafenib until radiologic progressive disease or an unacceptable toxicity occurs, at the discretion of the Investigator.

Doses of mapatumumab may not be altered.

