9.2 Sample Size Rationale

A total of approximately 100 subjects will be randomly assigned to 1 of 2 arms and treated with either sorafenib + placebo or the 2-agent combination of sorafenib and mapatumumab at 30 mg/kg in a 1:1 ratio. A sample size of 50 subjects randomized and treated in each group is sufficient to estimate the median time to progression with a precision of approximately -1.9 M to +2.6 M relative to the observed median. In addition, a sample size of 50 patients per arm will provide 80% power to detect an improvement in TTP from 5.5 to 8.9 M with at a one-sided significance level of 0.10.

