7.3.1.3 Missing Disease Assessment(s)

If a subject has a completely missed assessment(s) followed by an assessment showing radiologic disease progression, then PD will be assigned at the target date of the first missed assessment following an assessment showing no progression. This target date is defined as 42 days after the previous disease assessment showing no progression. If a subject has a missed assessment(s) followed by an assessment showing no radiologic disease progression, then the assumption will be that the subject remained stable during the missed assessment(s).

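### On-treatment scans move with mapatumumab/placebo dose delays, so if delays differ between arms the more-delayed arm appears to progress slightly later

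*Protocol*

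**What the plan says.** **On treatment.** Protocol 6.8 has scans that "will be performed at the end of every 2 cycles" and allows them at most 5 days before the next cycle begins. The synopsis speaks of two 21-day cycles, but it also ties the scan to the start of the next cycle. Protocol 5.1.3 plans 21 days per cycle, so the nominal interval is 42 days.

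**Delays.** Protocol 5.1.4: "Mapatumumab/placebo may be delayed up to 2 weeks for toxicities considered related to mapatumumab", or where the investigator judges a delay to be in the interest of safety. SAP 6.2 sets each dosing target 21 days after the actual previous dose, so a delay shifts all later cycles.

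**Off treatment.** Table 6-1, footnote 12: before progression is documented, "disease assessments will be performed every 6 weeks", with a window of ±3 days.

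**Dating progression.** SAP 7.5 uses the date of the first test that shows progression. SAP 7.3.1.3 moves the date back only when an assessment was missed altogether: "This target date is defined as 42 days after the previous disease assessment showing no progression". A late scan keeps its actual date.

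**Checks planned.** SAP 6.2 describes dose delays by treatment group. SAP 7.6.2 compares the arms on time to each of the first four assessments.

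**The concern.** TTP is known only to the nearest scan, and the primary Cox model (SAP 7.1.2) takes the scan date as the event time. Any difference between arms in scan spacing therefore enters the primary comparison directly. Here the spacing depends on how well the blinded infusion is tolerated, because only mapatumumab/placebo delays move the cycle. If the mapatumumab arm had more delays, its progressions would be dated later with no difference in disease, and the test would lean in its favour. If the placebo arm had more, the test would lean the other way. The missed-scan rule adds an inconsistency: a scan skipped altogether can be dated back to day 42, while one taken four weeks late cannot.

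**Working it through.** **1. Design inputs and the plan's own figures.** Protocol 6.2 randomizes "in a 1:1 ratio to 1 of 2 treatment arms". Protocol 9.2 says that 50 per arm "will provide 80% power to detect an improvement in TTP from 5.5 to 8.9 M with at a one-sided significance level of 0.10", and gives a median "with a precision of approximately -1.9 M to +2.6 M relative to the observed median".

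- HR = 5.5/8.9 = 0.618 for exponential times.
- Events (Schoenfeld) = 4(1.2816 + 0.8416)²/(ln 0.618)² = 4 × 4.508/0.2317, or 78. Power at 78 events is 80.1%. The plan states no event count, so 78 is inferred.
- Precision: 0.5 ± 1.96 × 0.5/√50 gives survival limits of 0.361 and 0.639. On an exponential with median 5.5 months these are −1.94 and +2.58 months.

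Both stated figures reproduce, so an exponential model with median 5.5 months is a fair base.

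**2. How far one interval can stretch.** Two cycle starts at 14 days each: 42 + 2 × 14 = 70 days. The mean lag from true to observed progression is about half the interval, so it rises from 21 to 35 days. That is 14 days, or 14/30.44 = 0.46 months, which is 0.46/3.4 = 14% of the design gain (8.9 − 5.5 = 3.4 months). This is the upper bound.

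**3. Effect on the primary test.** Trials were simulated with a true median of 5.5 months in both arms, 50 per arm, and an unstratified logrank test at one-sided 0.10. Follow-up was assumed to be 12 to 24 months, from the 12-month lock condition in SAP 3 and the 24-month study estimate in Protocol 3.1. Delay rates are assumptions, since the documents give none. Some runs used delays of 1 to 14 days and others a fixed 14 days. Runs had 2,500 to 6,000 trials per scenario (simulation error about 0.004 to 0.006). Ranges are across runs.

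| Cycles delayed, one arm vs other | One-sided error |
|---|---|
| none | 0.095–0.101 |
| equal (including 10% vs 10% and 30% vs 30%) | 0.095–0.108 |
| 10% vs 20% | 0.103–0.107 |
| 10% vs 30% | 0.113–0.120 |
| 10% vs 50% | 0.117 |
| 0% vs 10%, 20% or 30% | 0.116–0.118 |
| 0% vs 50% | 0.112–0.134 |
| 0% vs 100%, 14 days each | 0.166–0.167 |

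The HR is 1.00 with no or equal delays, 0.97 to 0.99 at moderate imbalance, and 0.94 in the extreme case. The apparent gain in the median is 0.07 to 0.16 months in the runs with 1 to 14 day delays. With fixed 14-day delays in 10% to 50% of one arm's cycles it is 0.08 to 0.25 months, and 0.48 months if every cycle slips. The error rates do not rise steadily up to 50%, so differences of about 0.01 between rows are within simulation noise.

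**4. Check of the simulation.** With no delays and true medians of 5.5 and 8.9 months it gives 80.6% power, in line with the plan.

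**5. Reach of SAP 7.6.2.** Four nominal intervals are 4 × 42 = 168 days, or 168/30.44 = 5.5 months, the assumed control median. About half of control progressions would come later than the scans it examines.

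**The case against.** The strongest reply is that nothing in the documents predicts unequal delays. The same rules apply to saline placebo under blinding. Protocol 1.4.3 describes adverse events on single-agent mapatumumab as generally mild to moderate, and Protocol 1.6 finds the combination's safety consistent with sorafenib and the disease. This stands. A reader might infer that mapatumumab will be delayed more often and that the primary result is therefore biased towards it. The documents do not support that. In the Phase 1b study, 3 of 16 subjects had severe lipase elevation possibly related to mapatumumab or its interaction with sorafenib. That study as described reports no placebo comparison, and Protocol 5.2.2 lists lipase elevation for sorafenib too.

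The mechanism is also limited. A delay not resolved or resumed within 2 weeks ends mapatumumab/placebo. The study calendars of Amendments 01 and 02 (footnote 14) then put subjects on sorafenib alone on 6-weekly scans. If a scan is done before the next dose is postponed, the first interval can take only one delay (42 + 14 = 56 days), though later intervals can still take two. The simulation does not model stopping, so its heavier-delay rows probably overstate the effect.

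The size is modest for a Phase 2 trial tested at one-sided 0.10, and at 10% versus 20% it cannot be told apart from equal delays. That also stands.

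Finally, SAP 6.2 and 7.6.2 would make an imbalance visible. They would, but neither changes the TTP estimate or triggers another analysis, and SAP 7.1.3 contains no interval-censored or scheduled-date version.

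**Conclusion.** The dependence of scan timing on dose delays is in the text, and no planned analysis removes it. Its effect is conditional and small. With unequal mapatumumab/placebo delays at assumed rates of 10% versus 30% to 50% of cycles, one-sided error is about 0.11 to 0.12 against a nominal 0.10, with an HR of about 0.97 to 0.99. It reaches about 0.17 only if every cycle in one arm slips the full 14 days. With equal delays there is no bias. A reader might infer that scan timing alone could produce the planned 5.5 to 8.9 month difference. It could not, since even the extreme case shifts the median by about half a month. The sizes rest on assumed delay rates, exponential times, assumed follow-up and an unstratified logrank test in place of the adjusted Cox model. The direction, towards the more-delayed arm, does not depend on the delay rates chosen. This is a cheap improvement to the plan rather than a flaw that undermines it.

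**What to change.** Amend Protocol 6.8, the synopsis and Table 6-1 (footnote 12) so that all disease assessments before progression in the main study fall every 6 weeks (±3 days) from randomization, regardless of dose delays. The interval and window are those already used off treatment, and they agree with the 42 days in SAP 7.3.1.3.

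The cost is protocol wording plus some inconvenience. In delayed subjects, some scans would fall away from the dosing visit. So would the PK samples that Table 6-1 (footnote 5) ties to scan days, which changes their timing relative to dose.

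If scanning is already complete, add to SAP 7.1.3, before unblinding, one sensitivity analysis of TTP that is interval-censored or uses scheduled scan dates, and read it alongside the delay summary in SAP 6.2 and the timing comparison in SAP 7.6.2. This changes no visits.
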